	Commercially Confidential Informat	tion	
Occult Blood			
Cryptosporidium Antigen by EIA ^{10, 12}			

Period	Post-Study Follow-Up		
Visit Name	Post-Study Follow-Up Call		
Days	6 Month Phone Contact Commercially Confidential Information	12 Month Phone Contact on	
lgA			
	Commercially Confidential Informa	tion	
Evaluation of Clinical Signs and Symptoms ⁶			
CHIM Diary			
Standard of Care Drug Administration (Nitazoxanide) ⁸			
Concomitant medications			
Adverse Events	S ¹⁵	S ¹⁵	
•	Commercially Confidential Information	on	
Safety Follow-Up Call for Study Participants	S	s	
Study completion information			

Commercially Confidential Information

² Serum pregnancy tests at Screening and Day 28. Urine pregnancy test at Baseline.

³ Before ABO809 administration.

⁴ Participants should make every attempt to bring self-collected stool specimen to the clinic for each Outpatient Follow-Up visit. In the 24 hours prior to each Outpatient Follow-Up visit, all stools should be collected.

⁵ During screening, the first diarrheal stool, and the first diarrheal stool with relapse after clinical clearance will be tested for enteral pathogenic micro-organisms.

⁶ Includes number and frequency of diarrheal episodes, stool weight, volume, and grading (see Section 8.3.2, Section 8.4.1, and Appendix 1). Additionally, includes evaluation of nausea, vomiting, abdominal pain or discomfort, abdominal tenderness, abdominal rebound, abdominal distension, fecal urgency, diarrhea, flatulence, tenesmus, poor appetite, dehydration, fever, and electrolyte imbalance

⁸ Nitazoxanide to be administered per Prescribing Information (i.e. 500 mg every 12 hours for 3 days). Nitazoxanide administration will be captured on the standard concomitant medication page, and no specific CRF is required.

Page **50** of **81** Protocol No. CABO809A02101

Period	Post-Study Follow-Up	
Visit Name	Post-Study Follow-Up Call	
Days	6 Month Phone Contact	12 Month Phone Contact

¹¹ Additional tests can be done at the discretion of the Investigator e.g., in the case of dehydration.

Commercially Confidential Information

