12.1 Analysis sets

For all analysis sets, participants will be analyzed according to the dose of ABO809 (*C. parvum* oocysts, also referred to as "treatment").

The safety analysis set will include all participants that received ABO809.

The PD analysis set includes all participants with available safety, parasitological and clinical data and with no protocol deviations with relevant impact on PD data.

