2.2 Analysis sets

For all analysis sets, participants will be analyzed according to the dose of ABO809 received (*C. parvum* oocysts, also referred to as "treatment").

The full analysis set (FAS) and safety analysis set (SAF) will be comprised of all participants who took one dose of ABO809 during the treatment period.

The Pharmacodynamic (PD) analysis set includes all participants with available parasitological and clinical data and with no protocol deviations with relevant impact on PD data. Fecal stool samples will also be assessed for other enteric pathogens which may cause diarrheal illness. Any participant with a positive test for these other enteric pathogens will be excluded.

The protocol deviation codes are summarised in Appendix Section 5.6.

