2.4 Analysis supporting primary objective(s) (PD analysis set)

2.4.1 Primary endpoint(s)

The primary endpoint is *Cryptosporidium* infection up to Day 10 (inclusive). This is defined as detection of oocysts

- in at least one fecal sample at \geq 72 hours after ABO809 administration
- or sooner than 72 hours if associated with symptoms suggestive of diarrheal illness, in at least one fecal sample after ABO809 administration.

Fecal stool samples will be assessed for *Cryptosporidium* infection using a commercially available diagnostic EIA test and confirmed by DFA test if the EIA is positive. Tests will be performed at a CLIA certified laboratory. Samples that test negative for *Cryptosporidium* by EIA will be reported as negative for *Cryptosporidium* without confirmation by DFA.

To overcome stool-to-stool and day-to-day oocyst shedding variability, up to 3 consecutive stool specimens, produced about 3-4 hours apart and on the same day will be tested. If at least one of the stool samples is *Cryptosporidium* positive, the participant will be considered infected. Otherwise, the participant will not be considered infected.

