2.5 Analysis supporting secondary objectives

The secondary objectives of this study are to (1) evaluate the incidence and characteristics of diarrheal illness (PD analysis set), (2) to evaluate the time to onset and resolution of *Cryptosporidium* infection (PD analysis set), and (3) to assess the safety and tolerability of ABO809 (Safety analysis set).

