5.6 Rule of exclusion criteria of analysis sets

Table 5-6 Protocol deviations leading to exclusion

	9	
Analysis Set	Criteria that cause subjects to be excluded	
SAF	Not treated with study treatment;	
PD	Not having informed consent; Not treated with study medication;	
	Not meeting entry criteria;	
	No evaluable, parasitological and clinical data;	
	Use of prohibited medication or vaccination during the study;	

6 Reference

Clopper, C. J. and Pearson, E. S. (1934), "The Use of Confidence or Fiducial Limits Illustrated in the Case of the Binomial," *Biometrika*, 26, 404-413.

Collett, D. (1994), Modeling Survival Data in Medical Research, London: Chapman & Hall.

ICH E9(R1) Harmonized Guideline: addendum on estimands and sensitivity analysis in clinical trials to the guideline on statistical principles for clinical trials. Final version on 20 November 2019.

Toxicity Grading Scale for Healthy Adult and Adolescent Volunteers Enrolled in Preventive Vaccine Clinical Trials (2007). Guidance for Industry. U.S. Food and Drug Administration (Internet) Available from: (Accessed 09 July 2021).

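### The SAP drops participants positive for another enteric pathogen from the primary infection analysis, although post-dose testing is scheduled only on diarrheal stools and the protocol has no such exclusion

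*SAP*

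**What the plan says.** SAP 2.2 defines the PD analysis set and adds: "Fecal stool samples will also be assessed for other enteric pathogens which may cause diarrheal illness". The next sentence is the rule at issue: "Any participant with a positive test for these other enteric pathogens will be excluded". It sets no time window and makes no exception for a participant whose Cryptosporidium infection is confirmed.

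The PD set is the population for the primary analysis (heading of SAP 2.4). SAP 2.5 also assigns it to the objective to "evaluate the incidence and characteristics of diarrheal illness (PD analysis set") and to the timing of infection. SAP 2.2 defines a full analysis set of everyone dosed, but SAP 2.4 does not use it. SAP 2.4.4 and 2.4.5 plan no sensitivity or supplementary analysis of the primary endpoint.

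The testing schedule is in Protocol Table 8-1, footnote 5: "During screening, the first diarrheal stool, and the first diarrheal stool with relapse after clinical clearance will be tested for enteral pathogenic micro-organisms".

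Protocol 12.1 limits the PD set to participants with available data and "with no protocol deviations with relevant impact on PD data". It does not mention other pathogens. SAP Section 4 lists no change to the protocol-specified analyses.

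**The concern.** Everyone has a screening stool tested. After dosing, on the footnote's schedule, a participant who never passes a diarrheal stool has no panel test and cannot be removed by one. A participant who passes a single diarrheal stool can be. Entry to the primary analysis set therefore depends on something that happens after dosing and is closely tied to a secondary endpoint.

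The primary endpoint does not need this protection. Infection is defined by a Cryptosporidium EIA confirmed by DFA, and one positive stool is enough (SAP 2.4.1). A second pathogen may obscure why someone had diarrhea, but it does not undo confirmed shedding of the challenge organism. Because the rule has no time limit, a positive relapse stool after Day 10 would also delete a Day 10 result that was already complete.

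The study exists to estimate infection and illness incidence for later challenge studies, from about 30 participants per dose level. Valid results should not leave the denominator for a reason linked to outcome, with no planned primary analysis that would show the effect.

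**Working it through.** **Inputs**
- Infection 90% and clinical symptoms 70%: planning rates in Protocol 12.8.1 and 12.8.2. The 70% is used here for diarrheal illness.
- N = 30 per dose level: Protocol Section 3.
- Exact (Clopper-Pearson) interval: 1-sided 80% in Protocol 12.4.1 and 12.8, 2-sided 80% in SAP 2.4.2.
- Panel-positive share q among those tested: not in the documents. Assumed 5-20%.

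**The plan's own figures.** Take the largest count x with P(X ≥ x) ≥ 0.80, then the 0.20 quantile of Beta(x, N − x + 1).
- Infection, N = 30: x = 26 (probability 0.8245), limit 78.6%; stated 78%.
- Symptoms, N = 30: x = 19 (probability 0.8407), limit 0.5399; stated 53%.

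Both agree when cut to a whole percent and are not in dispute.

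**Who can be removed after dosing.** One stool of grade 3-5 counts as diarrhea (Protocol 8.3.2), and the first such stool is tested. Clinical illness needs at least two diarrheal events within 24 hours on at least two days (Protocol Section 3, SAP 2.1.1.1). The group at risk of removal is therefore everyone with any diarrheal stool, which is wider than the ill and is not the same as the infected.

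**Case A: only ill participants are tested, and all of them are infected.** The share removed is 0.7q.
- Infection = (0.9 − 0.7q)/(1 − 0.7q)
- Illness = (0.7 − 0.7q)/(1 − 0.7q)

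| q | removed of 30 | infection | illness |
|---|---|---|---|
| 5% | 1.05 | 0.865/0.965 = 89.6% | 0.665/0.965 = 68.9% |
| 10% | 2.1 | 0.83/0.93 = 89.2% | 0.63/0.93 = 67.7% |
| 20% | 4.2 | 0.76/0.86 = 88.4% | 0.56/0.86 = 65.1% |

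**The same case in whole participants**, starting from 27/30 infected and 21/30 ill, with the SAP's 2-sided 80% interval for infection:

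| removed | infection | 2-sided 80% interval | illness |
|---|---|---|---|
| 0 | 27/30 = 90.0% | 79.1-96.3% | 21/30 = 70.0% |
| 1 | 26/29 = 89.7% | 78.4-96.1% | 20/29 = 69.0% |
| 2 | 25/28 = 89.3% | 77.7-96.0% | 19/28 = 67.9% |
| 3 | 24/27 = 88.9% | 76.9-95.8% | 18/27 = 66.7% |

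**Case B: those removed had diarrhea but no Cryptosporidium infection.** Infection rises: one removed gives 27/29 = 93.1%, two give 27/28 = 96.4%.

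**Case C: diarrhea is equally common in infected and uninfected participants.** Removal takes the same share of each group, so the expected infection rate stays at 90.0%.

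**Case D: the participant removed had isolated diarrhea, not clinical illness.** Illness rises: 21/30 = 70.0% becomes 21/29 = 72.4%. In a mixed setting, with 80% having any diarrheal stool (assumption) and q = 10%, illness reads (0.7 × 0.9)/(1 − 0.08) = 0.63/0.92 = 68.5%. Case A gives 67.7% at the same q.

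**The case against.** **Attribution of illness.** The strongest defense concerns the illness endpoint. Protocol 1.1 presents the model as one in which diarrhea comes from a single pathogen, and the illness definition requires no Cryptosporidium result. Keeping co-pathogen cases may count illness that the challenge did not cause. This stands: which version is the main one is an estimand choice. It does not carry over to infection, which is organism-specific.

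**Direction.** A reader might infer that the rule pushes infection and illness rates down. The documents do not support that as a general statement. Removal follows diarrhea plus a positive panel, not infection or clinical illness, and Cases B to D show no change or a rise.

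**Size.** No document gives a panel-positive rate. Screening stool tests, the exclusion of recent travel-associated diarrhea (Protocol 5.2), the infection-controlled unit (3.2) and the food restrictions (6.2.4.1) may keep it low. The primary analysis is descriptive. The shifts in Case A are small beside the 79.1-96.3% interval for 27/30.

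**Dose decisions.** A reader might also infer that the rule distorts dose adjustment. Protocol 6.5.1 bases that review on its own definition of evaluable data, not on the PD set, so the rule does not enter it directly.

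**Text.** The table row carrying footnote 5 is not visible, the footnote does not say that no other stool is tested, and SAP 2.2 speaks of stool samples generally. The selectivity therefore rests on the footnote's wording. SAP 2.5.6 is blacked out and could hold a related secondary analysis.

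**Table 5-6.** The absence of the rule from SAP Table 5-6 adds little. That table lists protocol deviations, and a positive panel is not one. Protocol Section 12 also lets the SAP specify procedures further, but a new exclusion from the primary analysis set goes beyond detail and belongs in SAP Section 4.

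**Conclusion.** The concern holds in limited form. The SAP makes membership of the primary analysis set depend on post-dose diarrhea, allows a confirmed infection by Day 10 to be deleted at any later time, and does not declare this departure from Protocol 12.1.

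Under Case A the infection rate moves by 0.4 to 1.6 points and the illness rate by 1.1 to 4.9 points. These figures rest on an assumed 5-20% panel-positive share, the planning rates, and testing confined to participants who are both ill and infected. Other plausible mixes move either rate up or leave infection unchanged, so no one-way bias is claimed. The effect on the primary endpoint is likely small. The rule should still be fixed before database lock, because it discards valid primary results with no benefit to that endpoint.

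**What to change.** - In SAP 2.2, remove the co-pathogen exclusion for the primary infection analysis (2.4) and the infection secondaries (2.5). Keep every otherwise eligible dosed participant.
- For diarrheal illness, report the rate both with and without participants positive for another pathogen after dosing, and state in advance which version is the main one.
- Describe any exclusion that remains in SAP 2.2, with its time window, and list it in SAP Section 4 as a change from Protocol 12.1.

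The cost is SAP wording and one extra row in the illness table. No new data are needed.

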2.2.1 Subgroup of interest

Exploratory subgroup analyses for primary and secondary endpoints may be performed by age, sex and fecal indole at baseline.

2.3 Participant disposition (All participants), demographics, other baseline characteristics, prior, concomitant and rescue medications (Safety analysis set)

2.3.1 Participant disposition

The number of participants screened and screening failures will be presented. Information collected on screening failures are the demographic information, informed consent, and Inclusion/Exclusion pages. In addition, the reasons for screen failures will be provided.

The following disposition status will be summarized as the number and percent of participants

• who completed each period (i.e. screening, treatment, inpatient and outpatient follow up) and who discontinued each period prematurely (including the reason for discontinuation) will be presented for each treatment group and overall.

For each protocol deviation, the number and percent of participants for whom the deviation applies may be tabulated.

2.3.2 Demographics and other baseline characteristics

All data for background and demographic variables will be listed by ABO809 treatment group and cohort number for all participants. Summary statistics will be provided by ABO809

treatment group and cohort number. Relevant medical histories and current medical conditions coded using the Medical Dictionary for Regulatory Activities (MedDRA) dictionary will be listed and may be summarized by system organ class (SOC) and preferred term (PT) of the MedDRA dictionary and by treatment group.

Following demographic variables will be summarized:

- Age
- Sex (male, female)
- Race (Caucasian, Black, Asian, native American, Pacific Islander, unknown, other)
- Ethnicity
- Body weight
- Body height (cm)
- Body mass index (BMI)

Following disease characteristics at baseline will be summarized:

- Fecal indole concentration level
- Presence of anti-Cryptosporidium antibody in serum and saliva, if available

2.3.3 Study treatment / compliance

Each participant will be supervised while receiving their single dose of ABO809 and will be domiciled for a minimum of 10 days to support compliance with study requirements.

If vomiting occurs within 30 minutes of administration of ABO809, a second administration of ABO809, at the same dose, may be given. If a participant vomited following the original dose, but did not vomit following the replacement dose, the participant is considered fully dosed. If a participant vomited the original dose and did not receive a replacement dose, or vomited both the original dose and the replacement dose, the participant is considered not fully dosed. The number and percent of participants who vomited following ABO809 administration and were dosed a second time may be presented by ABO809 treatment group and cohort number.

2.3.4 Prior, concomitant and post therapies

Prior and concomitant medications will be coded according to the latest version of World Health Organization (WHO) Drug Reference List dictionary which employs the Anatomical Therapeutic Chemical (ATC). The number and percentage of participants taking prior and concomitant medications may be tabulated for each treatment by ATC class and PT. Concomitant rescue and other medications, procedures, and significant non-drug therapies may also be summarized by ABO809 treatment group and cohort number.

Prior medications are defined as drugs taken and stopped prior to first dose of study medication. Any medication given at least once between the day of first dose of study medication and the last day of study visit will be a concomitant medication, including those which were started before dosing and continued into the treatment period.

Rescue medication nitazoxanide

To minimize the risk of severe clinical illness, long-term asymptomatic shedding and recurrence of *Cryptosporidium* infection, nitazoxanide will be administered on Day 21 to all participants who receive ABO809 and develop a *Cryptosporidium* infection, whether or not clinical symptoms are observed.

Nitazoxanide will be administered at 500 mg by mouth every 12 hours with food for 3 days as per the U.S. Prescribing Information, under the clinical conditions outlined below. All participants who receive ABO809 and develop an infection (i.e. oocyst shedding after Day 3 or sooner if associated with symptoms of diarrheal illness), will receive nitazoxanide on Day 21 or as soon as results of EIA analysis (and confirmed by DFA if positive) of Day 17 sample becomes available whether or not they develop clinical symptoms. There are conditions under which participants may receive nitazoxanide earlier: (i) participants with diarrhea persisting until Day 10 will start nitazoxanide on Day 10, (ii) participants with severe diarrheal illness (≥ Grade 3 as per Toxicity Grading Scale for Healthy Adult and Adolescent Volunteers Enrolled in Preventive Vaccine Clinical Trials (2007)) may receive nitazoxanide unless deemed contraindicated by the Investigator irrespective of timing. Whenever nitazoxanide treatment is administered to participants experiencing clinical symptoms, participants may be domiciled at the discretion of the Investigator until free of clinical symptoms for ≥24 hours. A second course of nitazoxanide may be considered for participants with severe diarrhea or treatment failure following first course of nitazoxanide at the discretion of the Investigator. The duration of treatment will depend upon the participant's response to therapy.

Participants will not receive nitazoxanide if:

- they did not shed oocysts at any time after Day 3 and
- they did not have diarrhea between Day 1 and Day 21 and
- there was no diagnosis of cryptosporidiosis in any of the participant's household contacts between Day 11 and Day 21

The summary of the following characteristics may be provided by ABO809 treatment group and cohort number:

- Tabulation of number of participants who required nitazoxanide on Day 21 with confirmation that all 3 doses of nitazoxanide are taken on consecutive days
- Tabulation of number of participants who required nitazoxanide earlier or if the participant requires a second course of nitazoxanide
- Tabulation of number of participants who had evidence of infection or clinical symptoms after last dose of nitazoxanide

Other rescue medications (other antiparasitic drug(s) e.g. paromomycin alone or in combination with azithromycin) will be captured under rescue medication category.

In participants with severe diarrheal illness, oral and/or intravenous hydration, and replacement of electrolytes as needed, is expected as part of the standard of care management of adverse events (dehydration and severe diarrhea). Fluid replacement therapy will be recorded as a concomitant medication.

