Treatment with nitazoxanide: Nitazoxanide is a safe and well-tolerated drug approved in the United States to treat diarrhea caused by Cryptosporidium parvum. In a 2015 C. muris challenge study, two subjects with persistent oocyst shedding were successfully treated with nitazoxanide and the infection was resolved in both subjects, demonstrating the potential of nitazoxanide as a rescue drug (Chappell et al 2015). Following resolution of diarrhea, C. parvum infection may be associated with shedding of oocysts with a 21% relapse rate as suggested by the 1993 Milwaukee outbreak (MacKenzie et al 1995). Participants who develop an infection (i.e. oocyst shedding), with or without clinical symptoms will receive a standard 3-day course of nitazoxanide treatment per the U.S. Prescribing Information on Day 21. Given the variability in the onset and duration of oocyst shedding and clinical symptoms in healthy adults. administering nitazoxanide on Day 21 is considered appropriate to enable the full characterization of the study endpoints. Nitazoxanide may be administered earlier, based on clinical findings (see Section 3.3 and Section 6.2.3). Once initiated, nitazoxanide treatment is expected to decrease or eliminate any persistent oocyst shedding to safeguard participants, their household contacts and public health interests. Participants will be informed about reasons of nitazoxanide treatment to improve compliance, which will be recorded in a participant diary. Although nitazoxanide has proven efficacy in reducing oocyst shedding and acute diarrhea in 80-93% of treated participants, there have been no studies looking at the effect of nitazoxanide on the incidence of long-term oocyst shedding or sequelae of cryptosporidiosis. Given this background, Safety Follow-Up Calls will be conducted up to Day 56.

Adaptive study design: The goal is to maximize the incidence of infection. The study cohorts of approximately 10 participants each are designed to enable domiciling of participants in an inpatient unit with adequate infection control, isolation and monitoring. Cohorts are sequential to enable adjustment of the ABO809 dose from one cohort to the next for efficacy and safety reasons. After the Day 14 visit, a Dose Adjustment Data Review will be conducted for the

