6.2.3 Rescue medication

To minimize the risk of severe clinical illness, long-term asymptomatic shedding and recurrence of *Cryptosporidium* infection, nitazoxanide may be administered at 500 mg by mouth every 12 hours with food for 3 days as per the U.S. Prescribing Information, under the clinical conditions outlined below. Nitazoxanide is the standard of care for the treatment of cryptosporidiosis. In double-blind, controlled trials in adults and adolescents with diarrhea and with or without enteric symptoms caused by *C. parvum*, nitazoxanide administered at 500 mg BID for 3 days resulted in a 96% clinical response rate 4 to 7 days following the end of treatment. In this study, clinical response was defined as "no symptoms, no watery stools and no more than 2 soft stools within the past 24 hours" or "no symptoms and no unformed stools within the past 48 hours" (Romark 2017).

All participants who receive ABO809 and develop an infection (i.e. oocyst shedding after Day 3), will receive nitazoxanide on Day 21 or as soon as EIA analysis

of Day 17 sample becomes available whether or not they develop clinical symptoms. There are conditions under which participants may receive nitazoxanide earlier: (i) participants with diarrhea persisting until Day 10 will start nitazoxanide on Day 10, (ii) participants with severe diarrheal illness (≥ Grade 3 as per Toxicity Grading Scale for Healthy Adult and Adolescent Volunteers Enrolled in Preventive Vaccine Clinical Trials (2007)) may receive

nitazoxanide unless deemed contraindicated by the Investigator irrespective of timing. Whenever nitazoxanide treatment is administered to participants experiencing clinical symptoms, participants may be domiciled at the discretion of the Investigator until free of clinical symptoms for ≥ 24 hours.

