6.7.2 Instruction for prescribing and taking study treatment

Table 6-4 Dose and treatment schedule

Investigational / Control Drug (Name and Strength)	Dose	Frequency and/or Regimen
ABO809, 3x10 ⁶ CE/3m L	Approximate oocyst count 1x10 ³ - 1x10 ⁶	A single dose on Day 1

Investigational / Control Drug (Name and Strength)	Dose	Frequency and/or Regimen
Nitazoxanide (Rescue medication)	500 mg	Every 12 hours with food for 3 days

7 Informed consent procedures

Eligible participants may only be included in the study after providing (witnessed, where required by law or regulation), IRB/IEC-approved Informed Consent.

Informed Consent must be obtained before conducting any study-specific procedures (e.g. all of the procedures described in the protocol). The process of obtaining Informed Consent must be documented in the participant source documents.

Novartis will review the study site proposed Informed Consent form to ensure it complies with the ICHE6 GCP guidelines and regulatory requirements and is considered appropriate for this study. Any further changes to the proposed consent form suggested by the Investigator must be agreed to by Novartis before submission to the IRB/IEC.

Information about common side effects already known about ABO809 and nitazoxanide can be found in Section 4.5, the Investigator's Brochure (IB) and the USPI for nitazoxanide. This information will be included in the participant Informed Consent and should be discussed with the participant during the study as needed. Any new information regarding the safety profile of ABO809 that is identified between IB updates will be communicated as appropriate, for example, via an Investigator notification (IN) or an aggregate safety finding. New information might require an update to the Informed Consent and must be discussed with the participant.

As per Section 4.6, during a Public Health emergency as declared by Local or Regional authorities i.e. pandemic, epidemic, or natural disaster, that may challenge the ability to obtain a standard written Informed Consent due to limits that prevent an on-site visit, Investigator may conduct the Informed Consent discussion remotely (e.g. telephone, videoconference) if allowable by a local Health Authority.

Guidance issued by local regulatory bodies on this aspect prevail and must be implemented and appropriately documented (e.g. the presence of an impartial witness, sign/dating separate ICFs by trial participant and person obtaining Informed Consent, etc.).

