¹³ All participants, whether or not they are symptomatic, will be domiciled in a unit until completion of Day 10 assessments. Participants who experience symptoms will remain domiciled for the duration of the diarrheal illness up to a maximum of Day 21. If a participant experiences diarrhea after Day 10 (after the participant has been discharged from the study site), the participant may be readmitted, at the discretion of the Investigator, to remain domiciled until the cessation of symptoms or Day 21. whichever is earlier.

¹⁴ CHIM diary eCRF page will capture only if the diary was fully complete or not. No data from the diary will be recorded on this diary eCRF page. AEs will be captured on the standard AE eCRF, and nitazoxanide administration will be captured on the standard concomitant medication eCRF page.

¹⁵ Adverse events of special interest (AESI) defined in Section 10.1.1.1 will be recorded at the 6 and 12 month Post-Study Follow-up calls as source data and reported to Novartis Safety if the Investigator considers there is a reasonable possibility that ABO809 caused the event, unless otherwise specified by local law/regulations.

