10.1.5 Reporting of study treatment errors including misuse/abuse

Medication errors are unintentional errors in the prescribing, dispensing, administration or monitoring of a medicine while under the control of a healthcare professional, participant or consumer (EMA definition).

Misuse refers to situations where the medicinal product is intentionally and inappropriately used not in accordance with the protocol.

Abuse corresponds to the persistent or sporadic, intentional excessive use of a medicinal product, which is accompanied by harmful physical or psychological effects.

Nitazoxanide errors and uses outside of what is foreseen in the protocol will be recorded on the appropriate eCRF irrespective of whether or not associated with an AE/SAE and reported to Novartis Safety only if associated with an SAE. Misuse or abuse will be collected and reported in the safety database irrespective of being associated with an AE/SAE within 24 hours of Investigator's awareness.

Table 10-1 Guidance for capturing the nitazoxanide errors including misuse/abuse

Treatment error type	Document in Dosing eCRF (Yes/No)	Document in AE eCRF	Complete SAE form
Unintentional nitazoxanide error	Yes	Only if associated with an AE	Only if associated with an SAE
Misuse/Abuse	Yes	Yes	Yes, even if not associated with a SAE

For more information on AE and SAE definition and reporting requirements, please see Section 10.1.1 and Section 10.1.2.

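### The SAP's optional nitazoxanide compliance table checks for three doses, while the regimen in the same section comes to six, and no routine per-dose record is described to support the check

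*SAP*

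**What the plan says.** **Regimen.** SAP 2.3.4, under the rescue medication heading: "Nitazoxanide will be administered at 500 mg by mouth every 12 hours with food for 3 days". Protocol 6.2.3 has the same: "nitazoxanide may be administered at 500 mg by mouth every 12 hours with food for 3 days". Protocol Table 6-4 lists the frequency as "Every 12 hours with food for 3 days", and footnote 8 to Table 8-1 repeats the 12-hourly, 3-day schedule.

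**Check.** Further down SAP 2.3.4 is a list of summaries that may be produced by treatment group and cohort. The first counts participants who needed nitazoxanide on Day 21, with "confirmation that all 3 doses of nitazoxanide are taken on consecutive days". The second counts those treated before Day 21 or given a second course, with no dose confirmation attached.

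**Records.**
- Protocol 4.1 says participants will be told the "reasons of nitazoxanide treatment to improve compliance, which will be recorded in a participant diary".
- Table 8-1 footnote 14 limits the CHIM diary eCRF page to whether the diary was fully completed: "No data from the diary will be recorded on this diary eCRF page". It sends nitazoxanide administration to the concomitant medication page.
- Table 8-1 footnote 8 agrees: "Nitazoxanide administration will be captured on the standard concomitant medication page, and no specific CRF is required".
- Protocol 10.1.5 requires nitazoxanide errors to be recorded on an eCRF whether or not an adverse event occurred. Table 10-1 has a column whose heading begins "Document in Dosing eCRF (Yes/No", answered yes for unintentional errors and for misuse or abuse.
- Protocol 6.7.1.1 asks participants to return unused nitazoxanide and packaging.

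**The concern.** The SAP states a regimen and then checks intake against half the number of doses it implies. A programmer working from that bullet would flag a participant as having taken every dose after three administrations.

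The bullet also promises a dose-level confirmation without saying which data supply it. The protocol describes no routine per-dose record in the database, and it names two different eCRF pages for nitazoxanide information.

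What is at stake is interpretation. Two adverse events of special interest concern symptoms or shedding that persist after treatment (Protocol 10.1.1.1), and SAP 2.3.4 has a separate summary of infection or symptoms after the last nitazoxanide dose. Someone reading those outputs will want to know whether the course was taken. A compliance table that calls half a course complete would mislead on that question.

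**Working it through.** **Inputs.** Dosing interval 12 hours, duration 3 days, 500 mg per dose (SAP 2.3.4; Protocol 6.2.3, Table 6-4, Table 8-1 footnote 8). Dose count in the check: 3 (SAP 2.3.4).

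**Doses in the stated regimen.** (24 h / 12 h) × 3 days = 6 administrations, or 6 × 500 mg = 3000 mg.

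**Attempt to reproduce the SAP's 3.**
- One dose a day: 1 × 3 = 3. This matches the count, but no section states once-daily dosing.
- Counting days of dosing instead of doses: 3. This also matches, so the bullet may be a slip for three days.
- The regimen as written gives 6, so the figure is not reproduced.

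**Size of the mismatch.** 3 / 6 = 0.50; 3 × 500 mg = 1500 mg out of 3000 mg.

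**Does the reference to consecutive days rescue the count?** Three doses 12 hours apart span 2 × 12 = 24 hours and touch two calendar days. Three doses spread over three calendar days fit once-daily intake only. Either pattern passes the literal check, and both are half the stated course. Six doses 12 hours apart span 5 × 12 = 60 hours. That covers three calendar days from an 08:00 start and four from a 20:00 start, so replacing doses with days would still leave an evening start ambiguous.

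**Where the confirming data would come from.**

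| Source | What the protocol says it holds | Enough to confirm dose count? |
|---|---|---|
| Participant diary (4.1) | Compliance | Possibly, but its content does not go onto the diary eCRF page |
| Diary eCRF page (footnote 14) | Whether the diary was complete | No |
| Concomitant medication page (footnotes 8, 14) | Nitazoxanide administration | Unknown; the fields are not listed |
| Dosing eCRF (Table 10-1) | Errors, misuse and abuse | Only when a deviation is recognised |
| Tablet return (6.7.1.1) | Unused drug and packaging | Possibly, but not linked to the analysis |

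I take the diary in Protocol 4.1 to be the CHIM diary, the only one described elsewhere. No row is named in the SAP as the source for the confirmation. Footnote 8 says no specific CRF is needed, whereas Table 10-1 assumes a dosing eCRF exists.

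**The case against.** The strongest reply is that this is a wording slip in an optional table. The regimen stands a few lines above the bullet, the mention of consecutive days suggests the author meant three days of dosing, and the SAP defines no completeness variable or threshold. The table covers Day 21 recipients only. All of that is fair, and it limits the weight of the point. It does not remove the contradiction: the bullet is the only instruction given for the confirmation, and it is wrong as written against the stated regimen.

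A second reply is that nitazoxanide data do reach the database. A reader might infer from footnote 14 that dose intake is never captured. The documents do not support that. The nitazoxanide row of Table 8-1 carries an X, which Section 8 defines as recorded in the clinical database. Footnotes 8 and 14 name the concomitant medication page, and 10.1.5 sends recognised errors to an eCRF. What stands is narrower: no routine per-dose record is described, and the detail held on the concomitant medication page cannot be judged from these documents.

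A third reply is that nothing downstream uses the three-dose check. That is correct. The persistence events in Protocol 10.1.1.1 follow from treatment having been given, a second course is at the investigator's discretion, and SAP 2.4.3 and 2.5.3 act on the start or taking of rescue medication, not its completion.

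**Conclusion.** The contradiction is certain: six administrations stated, three checked, a ratio of 0.50. The missing data source and the two differently named eCRF pages are real but lesser faults. Severity is minor. The effect is confined to one optional descriptive table for Day 21 recipients and to how persistence after nitazoxanide is read. Routine Day 21 dosing falls after the Day 10 primary window, and the censoring and set-to-missing rules do not depend on course completion.

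A reader might go further and estimate how many participants would be misread as treatment failures, by applying the protocol's nitazoxanide response figures to everyone infected. The documents do not support such a number. The 96% in Protocol 6.2.3 is clinical response in patients with diarrhea. The 80-93% in Protocol 4.1 combines reduced shedding with acute diarrhea. Day 21 treatment goes to anyone who became infected, yet Protocol 4.1 expects infection to resolve by Day 21, with excretion beyond 28 days in only 5%. Most recipients should have little left to clear, so no count is given here.

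The conclusion assumes only that the bullet is applied as written. It takes no view on which regimen is right.

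**What to change.** - In SAP 2.3.4, reconcile the dose count in the tabulation with the regimen stated in that section and in Protocol 6.2.3, Table 6-4 and Table 8-1 footnote 8. Express the check as a number of administrations; if days are used, say how an evening start is counted.
- Name the data source for the confirmation, for example the diary together with the tablet return in Protocol 6.7.1.1. If the concomitant medication page lacks them, add the number of tablets taken and the date and time of the first and last dose.
- Make Table 8-1 footnote 8 and Table 10-1 name the same eCRF page for nitazoxanide.

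The cost is one corrected phrase in the SAP, one aligned reference in the protocol and, if needed, two or three fields on an existing page with a little extra data entry. Splitting the persistence events by complete versus incomplete course would be a preference and is not needed to resolve this point.
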